### Abstract

**Background:** The most common issue associated with aging is frailty, which has a significant impact on the physical performance and immunity of older adults. Exercise is the primary modality in medical rehabilitation. The Indonesian Strong and Balanced Healthy Exercise (SI Kumbang) gymnastic exercise is a newly designed exercise model developed by researchers, which is a type of low-impact aerobic exercise with moderate intensity. SI Kumbang exercises are performed three times a week for 30 minutes over a period of 12 weeks. The main basis of these exercises is foot movements that follow a rhythm, with the feet rotating in sequence in the four cardinal directions.

**Objective:** This study aimed to evaluate and compare the impact of SI Kumbang gymnastic exercises and Bugar Lansia gymnastic exercise programs on physical performance and immunity in elderly.

**Methods:** A randomized single-blind clinical trial involved 66 elderly participants aged 60–70 years, divided into SI Kumbang (n=33) and Bugar Lansia (n=33) groups. Each group exercised three times weekly for 12 weeks. Outcomes measured for physical performance were cardiorespiration endurance using Six-Minute Walk Distance (6MWD), strength muscle using handgrip JAMAR, balance using Short Physical Performance Battery (SPPB), physical activity using Physical Activity Scale for the Elderly (PASE). Outcomes measured for immunity were inflamasome using Caspase-1 and IL-18. Data were analyzed using SPSS 29.0 tests with significance set at  $p<0.05$ .

**Results:** Physical performance in elderly showed, SI Kumbang group had significantly impact in cardiorespiration endurance (6MWD) ( $p=0.005$ ) and physical activity (PASE) ( $p=0.001$ ). However, there was no significant impact on strength muscle (handgrip JAMAR), and balance (SPBB). Immunity in elderly

showed, both group there were no significant in inflamasome Caspase-1 ( $p=0,055$ ) and IL-18 ( $p=0,255$ ).

**Conclusion:** In conclusion, SI Kumbang gymnastic exercise group has more significant impact in terms of physical performance, particularly in enhancing cardiorespiration endurance and physical activity rather than Bugar Lansia gymnastic exercise group. And there is no difference in physical performance aspects such as muscle strength, balance, and immunity aspects as Caspase-1 and IL-18 in the elderly.

**Keywords:** elderly, physical performance, immunity, SI Kumbang exercise gymnastics.

## INTRODUCTION

The number of people in the world who are 60 years of age or older is currently increasing, making up nearly 7% of the community. In both industrialized and emerging nations, the number of elderly people is increasing quickly. In 2020, 727 million people worldwide were 65 years of age or older. The number of elderly people in Indonesia has increased significantly over the past 50 years. During this period, the proportion of elderly people in Indonesia has doubled compared to the previous period. In 2021, the proportion of elderly people reached 10.82%, or approximately 29.3 million people. This figure indicates that Indonesia has entered a phase of an aging population structure, marked by the proportion of people aged 60 and over in Indonesia exceeding 10% of the total population. In fact, according to projections from the Central Statistics Agency (BPS), by 2045, the number of elderly people in Indonesia is estimated to reach almost one-fifth of the total population and is expected to continue to increase.

The most common issue associated with aging is frailty, which has a significant impact on the physical performance and immunity of older adults. Furthermore, skeletal muscle mass and strength decline with age, thereby diminishing physical autonomy. This decrease raises the chance of illness, disability, and functional limitations—all of which are referred to as frailty—which have an adverse effect on one's physical, mental, and social well-being. Reduced muscle strength, endurance, and physiological function are common characteristics of physically frail older persons, which raises their risk of poor health outcomes, functional decline, hospitalization, and death.

A key component of medical rehabilitation is exercise, which serves as the foundation for efficient treatment to stop pre-frail from becoming frail. Exercise training can enhance walking speed and physical performance in pre-frail older subjects, according to systematic reviews and meta-analyses. The advantages of many types of exercise, both at home and in groups, have been investigated for senior citizens.

Aerobic exercise is one type of exercise that can help stop muscle loss. The heart and lungs must work harder during aerobic exercise to meet the increased demand for oxygen. Dance-style rhythmic movements use the aerobic energy system to work major muscles while adhering to the chosen music. This creates rhythmic patterns, duration, and continuity that are intended to enhance and sustain bodily performance. Exercises that utilize dance movements is aerobic exercise performed through low-impact dance moves. If performed consistently for 30 to 60 minutes, the leg movements simply consist of variants of walking on the spot rather than many hops, making it safe for beginners and people of all ages and preventing knee and back injuries.

Numerous physical exercise regimens have been created to address the deterioration of functional capacity in the elderly. Among these are the SI Kumbang and Bugar Lansia gymnastic exercises, which are planned workouts intended to enhance general physical function, strength, and mobility. There is, however, little data comparing the efficacy of these two therapies. Bugar Lansia gymnastic exercise is one form of exercise that is appropriate for senior citizens in Indonesia. Seniors can benefit from Bugar Lansia, a mild, simple, and non-strenuous type of exercise. Bugar Lansia is a set of organized, consistent physical exercises that preserve and enhance mobility, which enhances quality of life. Bugar Lansia is a moderate-intensity exercise known to have a positive effect on improving functional movement in the elderly through assessments.

Additionally, Indonesia offers a wide range of well-liked modern dances that are appropriate for moderately strenuous exercise. One such dance is the Poco-Poco dance, which evolved into the gymnastics exercise of SI Kumbang. This local culture-based gymnastics is quite simple to execute and offers several health advantages, including increased blood vessel elasticity, circulation, oxygen intake,

balance, coordination, and muscle strength. SI Kumbang gymnastics exercise is ideal for senior citizens due to its distinctive low-impact motions and music, which can enhance physical fitness. Elderly quality of life is often improved by moderate-intensity gymnastics training, which also delays the beginning of various diseases. In addition, this activity can help maintain optimal cardiorespiration endurance, muscle strength, balance, physical activity and immunity. In order to ascertain whether intervention offers more advantages for geriatric health, immunity and physical performance in elderly groups, this study compares the effects of SI Kumbang gymnastics exercise and Bugar Lansia gymnastics exercise on physical performance and immunity in the elderly.

## METHODS

This study was designed as a randomized clinical trial with allocation concealment and single blinding to assess how the "SI Kumbang" gymnastic exercise and the "Bugar Lansia" gymnastic exercise model affected physical performance and immunity in elderly. In cooperation with the Rehabilitation Medicine Polyclinics, the 12-week intervention took place at the Ahmad Dahlan Indoor Hall of RS Islam Jakarta Pondok Kopi, East Jakarta, between April until September 2025. According to the FI-40 score, the target demographic was made up of senior citizens who were categorized as robust and pre-frail. Patients who visited the Rehabilitation Medicine Polyclinics at RS Islam Jakarta Pondok Kopi during the study period were included in the accessible population.

Female participants between the ages of 60 and 70 who met the following inclusion criteria were categorized as pre-frail (FI-40 score  $> 0.08 < 0.25$ ) or robust (FI-40 score  $\leq 0.08$ ) and had a body mass index (BMI) between 18.5 and 24.9. Participants had to have managed diabetes mellitus (GDS  $\leq 120$  mg/dL) and blood pressure ( $\leq 130/80$  mmHg) without taking any drugs that affected heart rate. Only those who were willing to participate, able to adhere to the study procedures, and had not been enrolled in any organized exercise program in the previous three months were included. Chronic heart or lung conditions, chronic conditions that cannot be reversed (e.g., cancer or chronic renal disease), diabetes complications in the extremities, motor impairment (MMT  $< 5$ ), knee pain, lower limb deformities

(genu varus/valgus), and hand deformities were among the exclusion criteria. Dropouts were defined as those who did not finish the study, missed more than six workouts, or had negative outcomes linked to the intervention.

A sample size of 33 people per group was determined. The study supervisor oversaw the use of a basic randomization program to carry out the random allocation. The Sequentially Numbered, Opaque, Sealed Envelope (SNOSE) technique was used to guarantee allocation concealment. Outcome assessors were subjected to single blinding; they were not told about group allocations and were not allowed to look for relevant information. The "SI Kumbang" and "Bugar Lansia" gymnastics exercise regimens were part of the intervention groups. For 12 weeks in a row, both therapies included three 30-minute sessions per week. Participants received adaption sessions to acquaint themselves with the workout regimens throughout the first week. The Borg Scale was utilized to track intensity.

The Six-Minute Walk Distance (6MWD) for cardiorespiratory endurance, and handgrip strength muscle measured using a handgrip JAMAR. The Physical Activity using Physical Activity Scale for the Elderly (PASE) questionnaire, the balance using Short Physical Performance Battery (SPPB) were among the outcome measures and the immunity aspect using inflammasome marker Caspase-1 and IL-18. The research team reviewed patient logbooks at the beginning of each week to track adverse effects such weariness, shortness of breath, pain, or dizziness. At RS Islam Jakarta Pondok Kopi, every suspected adverse event was swiftly assessed, and any required medical attention was given. Every adverse event was reported to the ethics committee of the institution.

Data analysis was performed using SPSS 29.0 tests with significance set at  $p<0.05$ . Descriptive summaries of the sample characteristics were provided. Prior to analysis, the normality of the data was checked. Dependent t-tests were used to compare pre intervention and post intervention score in the SI Kumbang and Bugar Lansia groups for normally distributed outcomes (6MWD, handgrip, SPPB, PASE, Caspase-1, IL-18); the Wilcoxon test was used to assess non-normal data. Independent t test or Mann-Whitney U test is used for compared the effectiveness of the two interventions ( $\Delta$  score). A p-value of less than 0.05 was deemed significant.

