## RESULT

A total of 66 elderly participants in the study, divided into the "SI Kumbang" and "Bugar Lansia" gymnastic exercise group. Table 1 summarizes the baseline characteristics of the subjects. Both groups have similar characteristics.

Table 1. Baseline Characteristics

| Characteristics               | Si Kumbang
(n=33) | Bugar Lansia
(n=33) |
|-------------------------------|----------------------|------------------------|
| Age (years), mean (SD)        | 65,25 (3,25)         | 65,14 (2,99)           |
| Body Mass Index, mean (SD)    | 23,5 (22,7)          | 22,95 (21,6 – 24,2)    |
| Normal                        | 31 (86,1)            | 31 (86,1)              |
| Overweight                    | 5 (13,9)             | 5 (13,9)               |
| Gender, n (%)                 |                      |                        |
| Female                        | 36 (100,0)           | 36 (100,0)             |
| Living History, n (%)         |                      |                        |
| Alone                         | 8 (22,2)             | 5 (13,9)               |
| Husband                       | 25 (69,4)            | 30 (83,3)              |
| Childs                        | 2 (5,6)              | 1 (2,8)                |
| Siblings                      | 1 (2,8)              | 0 (0)                  |
| Educational Background, n (%) |                      |                        |
| No Education                  | 1 (2,8)              | 2 (5,6)                |
| Primary                       | 2 (5,6)              | 5 (13,9)               |
| Secondary                     | 5 (13,9)             | 3 (8,3)                |
| High School                   | 16 (44,4)            | 14 (41,7)              |
| University                    | 12 (33,3)            | 11 (30,6)              |
| Comorbid                      |                      |                        |
| Diabetes Mellitus             | 8 (22,2)             | 3 (8,3)                |
| Hypertension                  | 10 (37,8)            | 11 (30,6)              |
| Use of Diabetes Mellitus      | 8 (23,2)             | 3 (5,6)                |
| Medication                    |                      |                        |
| Use of Hypertension           | 10 (37,8)            | 11 (30,6)              |
| Medication                    |                      |                        |

SD (standard deviation)

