## DISCUSSION

This study is the first to test the new SI Kumbang gymnastics exercise. Randomization has been performed, and the baseline demographic and clinical characteristics of the two groups are not different, except for IL-18, which shows a difference and is adjusted using ANCOVA.

From the clinical baseline data, the clinical picture of 6MWD, balance, and physical activity is less than normal. This illustrates the condition of elderly people who are generally inactive or sedentary in Indonesian society, that these three physical performances have indeed declined in elderly people entering the age of 60-70 years. In general, they will experience a decline in physical condition and health, especially in healthy elderly people who are inactive in sports, sedentary, or with various chronic diseases.

Other studies analyzed the relationship between sedentary time and physical endurance in elderly. They compared 83 older adults aged 60-87 years. Physical activity (light, moderate, or vigorous) and sedentary time were assessed using ActiGraph® GT1M Accelerometers (Fort Walton Beach, FL, USA). The Senior

Fitness Test assesses five physical fitness components (aerobic endurance, muscular strength, agility/dynamic balance, flexibility, and BMI), and includes six tests: 6-min walk distance (meters); chair stand test (repetitions/30 s); arm curl test (repetitions/30 s); 2.44 m up and go test (seconds); chair sit and reach test (centimeters); and back scratch test (centimeters). Regarding physical endurance, when compared to the inactive group, the active group achieved higher average results on aerobic endurance (6 min walk distance), upper and lower limb strength (arm curl and chair stand test, respectively), agility/dynamic balance. Elderly people are more likely to experience frailty, which many of us mistakenly believe to be a natural aspect of aging. It might be challenging to diagnose frailty in daily life and to differentiate between frailty syndromes and the normalcy associated with age vulnerabilities.

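### FI-40 defines who may enter, but it appears in no baseline table and no between-arm analysis, so comparability on frailty is not shown

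*Combined protocol and SAP*

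**What the plan says.** METHODS makes the FI-40 score the entry classifier: "the target demographic was made up of senior citizens who were categorized as robust and pre-frail". Women at or below 0.08 count as robust; those above 0.08 and below 0.25 count as pre-frail. Both are eligible, so a score should exist for every participant.

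On allocation, METHODS says: "The study supervisor oversaw the use of a basic randomization program to carry out the random allocation". Sealed envelopes provided concealment. No strata, blocks or minimisation are described. On size: "A sample size of 33 people per group was determined".

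The between-arm comparison is an independent t test or a Mann-Whitney test on change scores, with this threshold: "A p-value of less than 0.05 was deemed significant". RESULT adds one adjusted analysis, an ANCOVA for IL-18.

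On comparability, RESULT says of Table 1: "Both groups have similar characteristics". DISCUSSION goes further: "the baseline demographic and clinical characteristics of the two groups are not different, except for IL-18".

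**The concern.** The variable that defines the population is the one a reader would look for first in a baseline table, and it is missing. The INTRODUCTION says frailty affects both physical performance and immunity, which are the trial's two outcome domains, and it presents exercise as a way to keep pre-frail people from becoming frail.

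Two things are at stake. First, the statement that the arms do not differ covers more than the tables show. If the frailty mix did differ, and if robust and pre-frail women respond differently to exercise, part of a between-arm difference could come from the mix. Second, even with perfect balance, a reader cannot tell whether the sample was mostly robust or mostly pre-frail, and so cannot judge to whom the CONCLUSION applies.

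**Working it through.** **1. Where FI-40 appears.**

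| Place | Content | FI-40? |
|---|---|---|
| METHODS, eligibility | robust and pre-frail cut-offs | yes |
| METHODS, randomisation | supervised program, sealed envelopes | no |
| METHODS, analysis | paired tests; t or Mann-Whitney on change | no |
| Table 1 | age, BMI, gender, living situation, education, comorbidity, medication | no |
| Table 2 | 6MWT, handgrip, SPPB, PASE, Caspase-1, IL-18 | no |
| Table 3 | change by arm, p-values, adjusted p for IL-18 only | no |

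**2. Are the Table 3 p-values unadjusted?** Inputs: the Table 3 means and SDs of change, n = 33 per arm. Formula: t = difference / √((SD₁² + SD₂²)/33), 64 degrees of freedom.

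- Handgrip: (1.14 − 2.06)/0.613 = −1.50, p = 0.138 (stated 0.136).
- PASE: (5.39 − 1.16)/1.192 = 3.55, p = 0.0007 (stated 0.001).
- Caspase-1: (−38945.33 + 24957.94)/7154 = −1.96, p = 0.055 (stated 0.055).

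These agree with plain t tests on 33 per arm, with no FI-40 term.

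**3. How large could a chance imbalance be?** The documents do not give the pre-frail share, so 30% to 70% is assumed, with unrestricted allocation and 33 per arm. The SD of the between-arm difference in share is √(2p(1 − p)/33):

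- p = 0.5: √(0.50/33) = 0.123
- p = 0.3 or 0.7: √(0.42/33) = 0.113

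Shares move in steps of 1/33, so a gap of at least 15 points means at least 5 women (5/33 = 15.2%), and of at least 20 points at least 7 women (7/33 = 21.2%). Exact probabilities from two independent binomials:

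| Assumed pre-frail share | Gap ≥ 15 points | Gap ≥ 20 points |
|---|---|---|
| 30% or 70% | 22.6% | 8.0% |
| 50% | 26.8% | 10.9% |

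If the arms are instead fixed at 33:33 and 20 to 46 of the 66 women are pre-frail, the hypergeometric ranges are 18% to 32% and 6% to 14%, depending on the exact total. With 36 per arm, the number to which most Table 1 counts sum, the binomial ranges are 16% to 20% and 5% to 8%.

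**4. What would such a gap do to the results?** For a 20-point gap to explain a whole between-arm difference, robust and pre-frail women would have to differ in mean change by difference/0.20:

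- 6MWD: (81 − 54)/0.20 = 135 m, using the difference in medians. The arms' entire median gains are 81 m and 54 m.
- PASE: (5.39 − 1.16)/0.20 = 21 points. The SDs of change are 4.38 and 5.26.

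For partial distortion, assume the two categories differ in response by 0.2 to 0.8 SD. A 20-point gap then shifts the comparison by 0.20 × 0.2 = 0.04 SD to 0.20 × 0.8 = 0.16 SD. For PASE the pooled SD is √((4.38² + 5.26²)/2) = 4.84, so the shift is 0.2 to 0.8 points, against an observed difference of 4.23.

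**5. Which population?** Table 1 is headed n = 33 per arm, but 36 women are counted as female in each arm, BMI categories sum to 31 + 5 = 36, and living situation sums to 36 in both arms. Education sums to 36 and 35. Table 3 fits 33.

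**The case against.** The strongest reply is that randomisation already deals with this. Chance imbalance in any covariate, tabulated or not, is part of what the p-values of 0.005 and 0.001 allow for, and a probability of imbalance worked out before the trial is not evidence that one occurred. That stands. A reader might infer that the 6MWD and PASE differences cannot be separated from a different frailty mix; the documents do not support this. No imbalance is shown, and step 4 shows that even a 20-point gap would need implausibly large differences in response to account for either result.

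The tables also give indirect reassurance. Baseline 6MWT (medians 344.75 and 353), handgrip (means 16.11 and 16) and SPPB (medians 9 and 9) are close, and these overlap with what frailty means physically. This stands too, though it is no substitute for the classifier itself. The IL-18 difference (medians 186.77 and 279.56) says nothing about FI-40.

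The INTRODUCTION can be over-read. It links reduced strength and endurance to people who are already frail, and FI-40 of 0.25 or more is outside eligibility. It describes levels, whereas the trial compares changes, and it does not say that robust and pre-frail women respond differently.

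It is also tempting to say that simple randomisation was used. The document calls the program basic and describes no restriction. An exact 33:33 split has probability C(66,33)/2⁶⁶ = 9.8% under coin tossing, so equal arms neither establish nor exclude it.

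None of this answers the missing row, the breadth of the comparability statements, or the unknown pre-frail share.

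**Conclusion.** The point holds as a gap in reporting and analysis. FI-40 decides entry, is absent from both baseline tables and every between-arm analysis, and yet the arms are described as not different except for IL-18. Comparability on frailty is therefore not shown rather than disproved, and the share of pre-frail women is unknown. It does not follow that the trial is biased or that the 6MWD and PASE findings fail.

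A gap of at least 15 points would arise in roughly one trial in four, and of at least 20 points in roughly one in ten. These figures rest on unrestricted allocation, 33 per arm and an assumed pre-frail share of 30% to 70%. If a gap exists, the realistic effect is a modest shift in the estimates. The change is worth making because it is almost free.

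**What to change.** 1. For each outcome, add a covariate-adjusted between-arm analysis: ANCOVA with the baseline value of that outcome and continuous FI-40. Use a rank-based or transformed version for 6MWD, SPPB and IL-18. Place it beside the existing tests and label it a post hoc sensitivity analysis.
2. Add FI-40 (mean, SD) and robust/pre-frail counts by arm to the baseline table. State whether the row describes 33 or 36 women per arm. A baseline significance test is not needed.
3. Limit the comparability statements in RESULT and DISCUSSION to the characteristics tabulated; they need not be deleted.

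Estimates within robust and pre-frail women are not essential: with 33 per arm they would be very imprecise.

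Cost: no new data, provided the screening scores were kept. Each covariate uses one degree of freedom, so two covariates take the residual from 66 − 2 = 64 to 66 − 4 = 62. The model is chosen after the results are known, hence the label. For outcomes now compared by Mann-Whitney, the sensitivity analysis puts a model in place of that test, which is more than adding one term.

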## CONCLUSION

Both SI Kumbang and Bugar Lansia gymnastic exercises improved physical performance in older adults, as shown by significant gains in cardiorespiration endurance and physical activity in elderly. And there is no difference in physical performance aspects such as muscle strength, balance, and immunity aspects as Caspase-1 and IL-18 in the elderly.

These study results indicate that although both exercise modalities are effective in enhancing physical performance in elderly, SI Kumbang appears to provide superior benefits, particularly in improving cardiorespiration endurance and physical activity in elderly.

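### Intervention-linked harm and poor attendance are grounds for dropout, how dropouts are analysed is not stated, and the tables suggest 3 women per arm were left out of the comparison

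*Combined protocol and SAP*

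**What the plan says.** All references are to the combined protocol and SAP.

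- **METHODS, dropout definition:** "Dropouts were defined as those who did not finish the study, missed more than six workouts, or had negative outcomes linked to the intervention". With three sessions a week for 12 weeks (36 sessions), the attendance ground applies to a woman who attends fewer than 30.
- **METHODS, sample size:** "A sample size of 33 people per group was determined". No effect size, power or dropout allowance accompanies it.
- **METHODS, analysis:** "Independent t test or Mann-Whitney U test is used for compared the effectiveness of the two interventions", applied to change scores. The section gives no analysis population, intention-to-treat statement or missing-data rule.
- **METHODS, safety monitoring:** "The research team reviewed patient logbooks at the beginning of each week to track adverse effects such weariness, shortness of breath, pain, or dizziness". It adds that suspected events were assessed and that all adverse events went to the ethics committee.
- **METHODS, blinding:** "Outcome assessors were subjected to single blinding; they were not told about group allocations". Nobody else is described as blinded.
- **RESULT:** Tables 1, 2 and 3 are headed n=33 per arm, but the counts in Table 1 add to 36 per arm. No dropout numbers, dropout reasons or adverse events are reported.
- **CONCLUSION:** "SI Kumbang appears to provide superior benefits, particularly in improving cardiorespiration endurance and physical activity in elderly".

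**The concern.** Two of the three dropout grounds, intervention-linked harm and more than six missed sessions, are post-randomisation events that the assigned programme can cause. On the wording, a woman who was harmed but completed every measurement would still be a dropout. If dropouts are not analysed, the arms compared are no longer the arms randomised. Each arm becomes the women who tolerated and attended their own programme. Equal losses in the two arms do not protect the contrast if the reasons differ.

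The rule also needs a judgement that the text does not define: which outcomes count as negative, and which of them are linked to the exercise. The text does not say who decides, and only the outcome assessors are described as blinded. Nothing stated therefore shields that decision from knowledge of the arm.

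At stake is the population to which the superiority statement on walking distance and physical activity applies.

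**Working it through.** **1. Table 1 denominators.** Sex is given as 36 (100,0) in each arm, and the BMI categories add to 31 + 5 = 36. Most percentages fit 36: 31/36 = 86.1%, 5/36 = 13.9%, 25/36 = 69.4%, 30/36 = 83.3%. With 33, the first would be 31/33 = 93.9%. A few cells fit neither denominator. For example, 10 is shown as 37,8, but 10/36 = 27.8% and 10/33 = 30.3%.

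**2. Table 3 t-tests, rebuilt from the reported mean (SD) of change.** With n per arm, SE = s_p × √(2/n), where s_p² = (s₁² + s₂²)/2, and df = 2n − 2. Tests are taken as two-sided, because METHODS does not state sidedness.

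| Outcome | Difference | s_p | p at n=33 | p at n=36 | p stated |
|---|---|---|---|---|---|
| Caspase-1 | −38945.33 + 24957.94 = −13987.39 | 29059.5 | 0.055 (t = −1.96) | 0.045 (t = −2.04) | 0.055 |
| Handgrip | 1.14 − 2.06 = −0.92 | 2.489 | 0.138 (t = −1.50) | 0.121 (t = −1.57) | 0.136 |
| PASE | 5.39 − 1.16 = 4.23 | 4.840 | 0.0007 | 0.0004 | 0.001 |

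Caspase-1 is the most informative row. It gives 0.059 at 32 per arm and 0.051 at 34, so only 33 matches. Handgrip fits 33 within rounding of its inputs and does not fit 36. PASE discriminates little. The comparison therefore fits 33 per arm while baseline counts 36, which leaves 72 − 66 = 6 women, or 6/72 = 8.3%.

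**3. Illustration for 6MWD.** Assumption: 3 omitted women per arm are returned. Only medians and quartiles are reported, so the stated Mann-Whitney p=0.005 is inverted (normal approximation, no ties).

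- z = 2.807 and SE = √(67/(12×33×33)) = 0.0716. So θ = P(SI Kumbang change > Bugar Lansia change) = 0.5 + 2.807 × 0.0716 = 0.701.
- At 36 v 36, SE = √(73/(12×36×36)) = 0.0685.
- New θ = (1089 × 0.701 + 99a + 99b + 9c)/1296. Here a is the win probability of SI Kumbang returnees against the original Bugar Lansia women, b that of the original SI Kumbang women against Bugar Lansia returnees, and c that of returnees against returnees.

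| SI Kumbang returnees | Bugar Lansia returnees | a, b, c | θ | z | p |
|---|---|---|---|---|---|
| typical | worst | 0.701, 1, 1 | 0.726 | 3.30 | 0.001 |
| worst | worst | 0, 1, 0.5 | 0.669 | 2.47 | 0.014 |
| worst | typical | 0, 0.701, 0 | 0.643 | 2.08 | 0.037 |
| worst | best | 0, 0, 0 | 0.589 | 1.30 | 0.19 |

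**4. Illustration for PASE (same assumption of 3 per arm).** The new arm mean is (33 × mean + 3 × assumed value)/36, and the SD is recomputed to include the returnees.

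- SI Kumbang returnees unchanged, Bugar Lansia returnees at their arm mean: SI Kumbang mean 33 × 5.39/36 = 4.94; difference 4.94 − 1.16 = 3.78; p=0.001.
- SI Kumbang returnees worse by 1 SD (−4.38), Bugar Lansia returnees at their arm mean: (177.87 − 13.14)/36 = 4.58; difference 3.42; p=0.005.
- As the previous case, but with Bugar Lansia returnees 1 SD above their mean (1.16 + 5.26 = 6.42): Bugar Lansia mean (38.28 + 19.26)/36 = 1.60; difference 2.98; p=0.016.

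**5. Caspase-1.** With Bugar Lansia returnees at their arm mean, p is 0.036 if SI Kumbang returnees have their arm mean, 0.12 if they are unchanged, and 0.25 if they worsen by 1 SD. The stated threshold is "A p-value of less than 0.05 was deemed significant", so this outcome can fall on either side of it.

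**The case against.** **Exclusion is not stated.** METHODS defines a dropout but never says that dropouts go untested or unanalysed. This objection stands as far as it goes. A reader might take it as established that harmed women were removed, but the documents do not say so. The 36-against-33 pattern supports some exclusion. It does not give reasons, and all six women could be ordinary non-completers. Table 1 is also imperfect evidence, given its inconsistent cells. The t-test reproduction does not depend on those cells.

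**Safety.** A reader might infer that the safety information is itself restricted to women who tolerated the exercise. The documents do not support this. METHODS describes weekly logbook review, assessment of suspected events and reporting of all adverse events to the ethics committee, with no exception for dropouts. No safety summary is presented that could be conditioned in this way. What can be said is narrower: RESULT gives no adverse events by arm.

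**Fragility.** A reader might infer that a few exclusions could overturn the headline result. The only scenario above 0.05 for 6MWD requires the omitted Bugar Lansia women to have the best gains of all. That does not fit women lost through harm or poor attendance. PASE stays significant in every scenario run. This objection stands.

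**Differential tolerance.** DISCUSSION says only SI Kumbang used a 0.5 kg hand weight, and INTRODUCTION describes Bugar Lansia as mild. Both programmes are also called moderate intensity. A tolerance difference is possible but not shown. Nor does the text equate the tracked symptoms with the negative outcomes that define dropout.

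The objections leave the core point untouched: the rule is in the text, its handling is unspecified, and the analysed numbers fall short of the baseline counts.

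**Conclusion.** The point holds in a limited form. Harm and poor attendance, which can be consequences of the assigned programme, are grounds for dropout, and nothing in the documents keeps these women in follow-up or analysis. The tables suggest that 3 women per arm (6 of 72, 8.3%) were left out of the comparison. That rests on Table 1's counts being the numbers randomised and on the t-tests being two-sided. Reasons by arm are not given, so the size and direction of any bias are unknown.

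On the assumption of 3 returned per arm, 6MWD p is 0.001 to 0.037 in the plausible scenarios (0.19 in the implausible one), and PASE p is at most 0.016. Caspase-1 is the outcome closest to the threshold: 0.055 at 33 per arm, and 0.045 at 36 with the means and SDs unchanged. The superiority claim is not shown to be wrong. What is unresolved is whether it describes the women randomised or only those who completed, tolerated and attended their programme.

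**What to change.** 1. Redefine intervention-linked harm and more than six missed sessions as recorded events. They should not be grounds for removal from outcome assessment or analysis. This concerns measurement and analysis only, not whether a woman continues the exercise.
2. State the analysis population: every randomised woman with a post-test, in her assigned arm. Restore any omitted woman who has one.
3. Report the number randomised, the number without post-test data by arm and reason (adverse event, attendance, other), and adverse events by arm. Reconcile the 36 in Table 1 with the n=33 headings.
4. Add a worst-rank sensitivity analysis for 6MWD and PASE, and keep the 33 v 33 result as supplementary.
5. If the omitted women have no post-test data, restrict the superiority statement in CONCLUSION to women who completed, tolerated and attended the programme.

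**Cost:** a change of wording, a participant-flow table, an adverse-event table, and a re-run of the between-group tests. No new patients or procedures are needed. The documents do not say whether post-tests exist for the omitted women. If they do not, rewording cannot recover them and step 5 applies. The downside is that the estimated effect may shrink slightly once less adherent women are included.
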